9.4.4 Timing of Analyses

9.4.4.1 Interim Safety Analyses

The blinded medical monitor, clinical program manager, unblinded medical monitor and PI of the clinical laboratory will review data through the Day 15 visit after vaccination 1 for the 4 subjects in the sentinel groups. After the completion of Group 1 enrollment, the SMC will then review the data on all Group 1 subjects through the post 2nd vaccination Day 15 visit. These reviews, however, may not involve any hypothesis testing and will not be considered in estimating the precision of any estimates made at the conclusion of the study.

9.4.4.2 Final Analyses

Clinical, safety, and reactogenicity data through approximately Day 57 after last study vaccination will represent the primary clinical database for the trial. Once all subjects have completed the Day 57 post dose 2 visit and the data are entered in the database, validated and monitored according to the clinical monitoring plan, the primary clinical database will be locked. Unblinded analyses of the primary and secondary safety, reactogenicity, and immunogenicity outcomes (Neutralization and viremia) and any supporting analyses of these outcomes described in the SAP will be performed by the SDCC and provided to the sponsor and PI. Individual subject listings will not be generated at this point. The laboratory staff that run the assays for the Day 180 post dose 2 visit will remain blinded, and the assessment of relationship to study product of any SAEs that may be reported at the Day 180 post dose 2 visit will be delegated to blinded sub-investigators at the clinical site. While the results will not be used to make any decisions concerning the conduct of this trial, they may be used to make decisions on activities external to this trial such as the design of future trials of this vaccine. Since this early analysis of the data is not intended to impact the conduct of the trial, it has no impact on Type I error and adjustments are not planned.

The remaining analyses, including generation of all individual subject listings, will be completed and the CSR generated after the last subject's last visit is completed, and the final clinical database, including all long-term safety follow-up data, is cleaned, monitored and locked.

A formal statistical analysis plan (SAP) will be developed and finalized prior to unblinding for any analysis, which defines the analyses to be included in the CSR.

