6.3.3 Blinding and Masking Procedures

This is a partially-blinded clinical trial.

Study staff and investigators will not be blinded to dose group but, within dose groups, subjects, investigators, and study staff other than unblinded site research pharmacist (or other designated unblinded personnel administering study product) will be blinded as to the subject's treatment assignment (vaccine vs. placebo). Laboratory personnel performing antibody assays will be blinded to dose group and treatment assignment.

The randomization scheme will be generated by the CC and provided to unblinded study personnel (i.e., research pharmacists performing study vaccination preparations and unblinded study vaccine administrators) at the clinical site.

An unblinded site research pharmacist will prepare the study product and an unblinded research nurse will inject the study product per the randomization assignment. The pharmacist will conceal the contents of the syringe by wrapping the syringe barrel with an overlay, opaque tape, or other equivalent material. In addition, the subject will be asked to look away when the vaccine is being administered.

The unblinded site research pharmacist and unblinded research nurse will not be involved in study-related assessments or have subject contact for data collection following study vaccine administration.

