8.5 Adverse Events and Serious Adverse Events

8.5.1 Definition of Adverse Events (AE)

Adverse event means any untoward medical occurrence associated with the use of an intervention in humans, whether or not considered intervention-related (21 CFR 312.32 (a)). An AE can therefore be any unfavorable and unintended sign (including an abnormal laboratory finding), symptom, or disease temporally associated with the use of medicinal (investigational) product.

Any medical condition that is present at the time that the subject is screened will be considered as baseline and not reported as an AE. However, if the severity of any pre-existing medical condition increases, it should be recorded as an AE.

Adverse events can be further divided into solicited adverse events and unsolicited adverse events. Solicited adverse events are those for which the study team will specifically query the participant whether they occurred. Unsolicited adverse events are those events that the subject report occurring without being queried about the specific event.

All AEs will be assessed for severity and relationship to study intervention (see Section [8.5.3.2](#)).

All AEs, solicited and unsolicited, will be captured on the appropriate data collection form. Information to be collected for AEs includes event description, date of onset, assessment of severity, relationship to study product and alternate etiology (assessed only by those with the training and authority to make a diagnosis and listed on the FDA Form 1572 as an investigator), date of resolution, seriousness and outcome. AEs occurring during the trial collection and reporting period will be documented appropriately regardless of relationship. In addition, all medically-attended adverse events (MAAEs) (i.e., events for which medical care from a healthcare provider is sought) will be collected through Study Visit 09.

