8.5.4 Time Period and Frequency for Event Assessment and Follow-up

For this study all solicited AEs will be documented for the 8 days following study product administration.

For this study, all unsolicited, non-serious AEs will be documented from Study Visit 01 (Day 1) through Study Visit 07 (Day 29 post second vaccination).

All MAAEs, SAEs and new onset chronic medical conditions (NOCMC) will be documented from Study Visit 01 (Day 1) through Study Visit 09 (final visit).

Resolution of an AE is defined as the return to pre-treatment status or as stabilization of the condition, with the expectation that it will remain chronic. Site PIs are required to follow all reported AEs until either resolution of the AE or until the event is stable, as determined by the site PI; all SAEs will be followed until either resolution

of the SAE or until the SAE is stable, as determined by the PI. Subjects who have an unresolved SAE at either the final study visit or at discontinuation of study participation will continue to be followed, with the subject's permission, until the SAE is stable/deemed chronic, as determined by the site PI.

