8.5.7 Adverse Events of Special Interest

This study will also assess New-Onset Chronic Medical Conditions (NOCMCs) from the day of receipt of the first dose of study product until study completion. NOCMCs are defined as any new ICD-10 diagnosis (10th revision of the International Statistical Classification of Diseases and Related Health Problems) that is applied to the subject during the course of the study, after receipt of the study agent, that is expected to continue for at least 3 months and requires continued health care intervention. NOCMCs will be assessed and recorded as unsolicited AEs.

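### After the Day 57 release of by-arm results to the PI, blinded causality assessment is reserved only for SAEs reported at the Day 180 visit, so late MAAEs and chronic conditions may be judged unblinded

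*Protocol*

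**What the plan says.** Protocol 9.4.4.2 locks a primary database after the last Day 57 post-dose-2 visit. Unblinded analyses of the safety and immunogenicity outcomes "will be performed by the SDCC and provided to the sponsor and PI". Three limits accompany the release:

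- On detail: "Individual subject listings will not be generated at this point".
- Laboratory staff running the Day 180 assays stay blinded.
- On causality, the site has blinded sub-investigators, to whom "assessment of relationship to study product of any SAEs that may be reported at the Day 180 post dose 2 visit will be delegated".

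SAP 6.3 repeats the release to the sponsor and PI and the withholding of listings. It contains neither the laboratory nor the causality safeguard.

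Safety collection continues after Day 57. Protocol 8.5.4 states: "All MAAEs, SAEs and new onset chronic medical conditions (NOCMC) will be documented from Study Visit 01 (Day 1) through Study Visit 09", the final visit. Protocol 8.5.1 requires: "All AEs will be assessed for severity and relationship to study intervention". Protocol 8.5.7 treats chronic conditions as the events of special interest: "NOCMCs will be assessed and recorded as unsolicited AEs".

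On who knows what, Protocol 6.3.3 says: "Study staff and investigators will not be blinded to dose group but, within dose groups", the vaccine-or-placebo assignment is masked.

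**The concern.** By naming blinded assessors, the plan accepts that the Day 57 release endangers blinded attribution. The protection is narrower than the data still being collected. MAAEs and NOCMCs run to the same visit and need the same judgements, but are not mentioned. The delegation also covers relationship only, not severity. Read literally, it is tied to SAEs reported at the Day 180 visit, which leaves out an SAE reported between the release and that visit.

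A PI who can infer a subject's arm could lean either way when grading or attributing a late event. Two things are at stake:

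- **Related-event summaries:** SAP Table 24, the related rows of Table 9, and Figures 7 and 9.
- **SUSAR determination:** Protocol 8.5.2.1 makes it depend on causality, and Protocol 8.5.6.2 attaches the 7- and 15-day reports to it.

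**Working it through.** The plan gives no figure on this question. Its only probability figures, in Protocol Table 8, reproduce (for example 1 − 0.85^10 = 80.3%) but do not enter here.

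**1. Is the PI excluded from judging late events?** No section does so.

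- Protocol 8.5.3 gives seriousness, severity and causality to any qualified on-site investigator.
- Protocol 8.5.6.1 gives SAE assessment to the principal investigator or a sub-investigator.
- Protocol 10.1.9.1 gives review of adverse events to the PI or a designee.

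The PI is therefore permitted to judge these events, but is not named as the one who will.

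**2. Can the PI infer treatment without listings?** Inputs: dose group is open (Protocol 6.3.3); allocation is 10 vaccine to 3 placebo in Group 1 and 10 to 2 in Group 2 (Protocol 6.1 and Table 1); the site records each subject's events. SAP Table 23 counts subjects by preferred term, with a separate column for each vaccine dose.

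Before any release, the chance of being on vaccine is 10/13 = 76.9% in Group 1 and 10/12 = 83.3% in Group 2.

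Suppose k subjects in one cohort report a term. If the dose column shows k, all had vaccine; if it shows 0, all had placebo. Either way all k arms are known. If the event is unrelated to arm, the chance of this is

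P(k) = [C(10,k) + C(p,k)] / C(10+p,k), with p = 3 or 2 placebo subjects.

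| k | Group 1 (10:3) | Group 2 (10:2) |
|---|---|---|
| 1 | 13/13 = 100% | 12/12 = 100% |
| 2 | (45+3)/78 = 61.5% | (45+1)/66 = 69.7% |
| 3 | (120+1)/286 = 42.3% | (120+0)/220 = 54.5% |

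The single-reporter result needs no assumption about independence from arm. Pooling placebo across cohorts does not hide it, because the dose columns are separate. Subjects with no distinctive term are not individually identified this way.

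**3. How long is the exposure?** The subject whose visit completes the milestone has 180 − 57 = 123 days left. The last Group 1 subject must have been enrolled at least 28 + 14 + 7 = 49 days before the last Group 2 subject: dose 2, then Day 15 after it, then the Group 2 sentinel Day 8 review. That leaves at most 123 − 49 = 74 days, allowing no time for committee review. Data entry, monitoring and lock come before release and shorten both.

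**4. What does one judgement weigh?** With 10 vaccine recipients per dose, reclassifying the only related event of one subject moves that arm's rate by 1/10 = 10 percentage points.

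**The case against.** The best defence is that the safeguard was matched to what matters.

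- **Endpoints.** The primary outcomes in Protocol section 3 count occurrences, without regard to relatedness. Laboratory toxicities end at Day 15 after dose 2; Grade 3 unsolicited and any-AE outcomes end at Day 29. Only SAEs run to study end, and those are what 9.4.4.2 protects. MAAE or NOCMC relatedness is not an endpoint, and no vaccination can be affected by then. This stands, and it limits the consequence.
- **Who judges.** A reader might infer that the PI will judge these events knowing treatment. The text does not say so: blinded sub-investigators will be on site and nothing prevents their doing it. But nothing requires it either.
- **What is released.** Neither document lists the Day 57 tables. Preferred-term tables by arm are a likely part of the supporting analyses, but this is an assumption.
- **Size.** Harm needs a distinctive earlier term, a later MAAE, NOCMC or SAE in the same subject, and the PI as assessor. That joint chance cannot be estimated from the documents, and late events among 25 healthy adults will be few. SAP Tables 25–27 stop at Day 57, and no table is dedicated to MAAEs or NOCMCs. That late events enter Table 24, Table 9 and Figures 7 and 9 is inferred from Protocol 8.5.7 and SAP 8.1.
- **SAEs between visits.** The Schedule of Assessments has no planned contact between Visits 08 and 09, so the Day 180 wording may be meant to cover the whole interval. That calls for a clarification.

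These points reduce the weight of the gap; none closes it.

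**Conclusion.** The point holds as a gap in a safeguard the plan already has. Following 9.4.4.2 as written permits a PI holding by-arm results to grade and attribute late MAAEs and NOCMCs and, on a literal reading, some late SAEs. If by-arm preferred-term tables are released, a sole reporter of a term in a cohort is identified with certainty. The 62% and 70% figures hold only for exactly two reporters and an event independent of arm. The 123 days is a ceiling.

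Two stronger readings are not supported. One is that the within-cohort blind is lost for everyone: listings are withheld, and only some subjects can be placed. The other is that the primary safety endpoints are biased through attribution: they do not use relatedness. What remains at risk is the severity and relatedness of a few late events, in the related-event summaries and in SUSAR decisions. This is a worthwhile low-cost improvement, not a flaw in the main conclusions.

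**What to change.** Make three matching edits:

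1. **Protocol 9.4.4.2:** extend the delegation to both severity and relationship, for every SAE, MAAE and NOCMC reported after release of the Day 57 results, with no reference to the visit at which it is reported.
2. **Protocol 10.1.9.1:** state that, for these events, the review assigned to the PI or a designee is done by a blinded designee.
3. **SAP 6.3:** repeat the safeguard beside the statement that the results go to the PI.

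The assessors are already in the plan. The cost is the text change and slightly more sign-off work for the blinded sub-investigators; visits, endpoints and sample size are unchanged. Withholding the results from the PI is not recommended, because SAP 6.3 gives research planning by the sponsor and PI as the purpose of the release.

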9.4.5 Sub-group Analyses

Sub-group analysis (e.g, analysis based on age, sex, race/ethnicity or other demographic characteristics) is not planned due to the limited size of this Phase 1 clinical study.

9.4.6 Tabulation of Individual participant Data

Individual participant data will be listed by measure and time point after the last subject's last visit is completed and the final clinical database, including all long-term safety follow-up data, is cleaned, monitored and locked.

10. SUPPORTING DOCUMENTATION AND OPERATIONAL CONSIDERATIONS

10.1 Regulatory, Ethical and Study Oversight Considerations

Each site principal investigator will obtain IRB approval for this protocol and any amendments to be conducted at his/her research site(s).

NTI must receive the documentation that verifies IRB/IEC-approval for this protocol, informed consent, and associated documents prior to the recruitment, screening, and enrollment of subjects.

10.1.1 Informed Consent Process

Informed consent is a process that is initiated prior to an individual agreeing to participate in a trial and continuing throughout the individual's trial participation. Before any study procedures are performed, informed consent will be obtained and documented. Subjects will receive a concise and focused presentation of key information about the trial, verbally and with a written ICF. The explanation will be organized and presented in lay terminology and language that facilitates understanding why one might or might not want to participate. The ICF must not include any exculpatory statements.

The site PI or their designee will describe the protocol to potential subjects face-to-face. The key information about the purpose of the trial, the procedures and experimental aspects of the trial, risks and discomforts, any expected benefits to the subject, and alternative treatment will be presented first to the subject.

Subjects will also receive an explanation that the trial involves research and a detailed summary of the proposed study procedures and study interventions/study products. This will include aspects of the trial that are experimental, the probability for random assignment to treatment arms, any expected benefits, all possible risks (including a statement that the particular treatment or procedure may involve risks to the subject or to the embryo or fetus, if the subject is or may become pregnant, that are currently unforeseeable), the expected duration of the subject's participation in the trial, alternative treatment/procedures that may be available, and the important potential benefits and risks of these available alternative treatment/procedures.

Subjects will be informed that they will be notified in a timely manner if information becomes available that may be relevant to their willingness to continue participation in the trial. Subjects will receive an explanation as to whether any compensation and any medical treatments are available if injury occurs, and, if so, what they consist of or where further information may be obtained. Subjects will be informed of the anticipated financial expenses, if any, to the subject for participating in the trial, as well as any anticipated prorated payments, if any, to the subject for participating in the trial. They will be informed of whom to contact (e.g., the site PI) for answers to any questions relating to the research project.

Information will also include the foreseeable circumstances and/or reasons under which the subject's participation in the trial may be terminated. The subjects will be informed that participation is voluntary and that they are free to withdraw from the study for any reason at any time without penalty or loss of benefits to which the subject is otherwise entitled.

The extent of the confidentiality of the subjects' records will be defined, and subjects will be informed that applicable data protection legislation will be followed. Subjects will be informed that the monitors, auditors, IRB, NTI, and regulatory authorities will be granted direct access to the subject's original medical records for verification of trial procedures and/or data without violating the confidentiality of the subject, to the extent permitted by the applicable laws and regulations, and that, by signing a written ICF, the subject is authorizing such access.

Subjects will be informed that records identifying the subject will be kept confidential and, to the extent permitted by the applicable laws and/or regulations, will not be made publicly available and, if the results of the trial are published, the subject's identity will remain confidential. Subjects will be informed whether private information collected from this research and/or samples/specimens will be used for additional research, even if identifiers are removed.

Subjects will be allowed sufficient time to consider participation in the trial and have the opportunity to discuss the trial with their family, friends or legally authorized representative, or think about it prior to agreeing to participate.

ICFs will be IRB-approved and subjects will be asked to read and review the ICF. Subjects must sign the ICF prior to starting any study procedures being done specifically for the trial.

Once signed, a copy of the ICF will be given to the subjects for their records. The subject(s) may withdraw consent at any time throughout the course of the trial. The rights and welfare of the subjects will be protected by emphasizing to them that the quality of their medical care will not be adversely affected if they decline to participate in or withdraw from the trial.

New information that significantly impacts the subject's risk of receiving the study interventions/study products will be communicated by the site PIs or their designees to the subjects who consent to participate in the trial in accordance with IRB requirements. The ICF will be updated and subjects will be re-consented in accordance with IRB requirements, if necessary. Subjects will be given a copy of all ICFs that they sign.

Study personnel may employ IRB-approved recruitment efforts prior to obtaining study consent if a patient-specific screening consent is on record or if the IRB has agreed that chart review is allowed without a fully executed screening consent. In cases where there is not a patient-specific screening consent on record, Clinical Staff may pre-screen via chart review and refer potential subjects to the Research staff. Research staff would obtain written consent per the standard informed consent process before conducting protocol-specific screening activities.

10.1.1.1 Requirements for Permission by Parents/Guardians and Assent by Children (in case of a minor)

Not applicable.

10.1.1.2 Other Informed Consent Procedures

Not applicable.

10.1.1.3 Ethical Standard

The PI will ensure that this trial is conducted in full conformity with principles of the Belmont Report: Ethical Principles and Guidelines for the Protection of Human Subjects of Research (National Commission for the Protection of Human Subjects of Biomedical and Behavioral Research [April 18, 1979]) and codified in 45 CFR 46, 21 CFR 50 and 21 CFR 56, as applicable. The site PIs will also ensure conformity with ICH E6 GCP and applicable federal regulations, guidance and guidelines for GCP and Clinical Trials with humans.

10.1.1.4 Institutional Review Board

The institution engaged in this research will hold a current Federalwide Assurance (FWA) issued by the Office for Human Research Protections (OHRP) for federally funded research. The IRB must be registered with OHRP [OHRP-only or OHRP/FDA] as applicable to the research. The IRB FWA number will be provided to NTI.

The site PI will obtain IRB approval for this protocol to be conducted at his/her research site(s) and send supporting documentation to NTI before initiating recruitment of subjects. The site PI will submit applicable information to the IRB on which it relies for the review, to conduct the review in accordance with 45 CFR 46, ICH E6 GCP guidelines, and as applicable, 21 CFR 56 (Institutional Review Boards), 21 CFR 50 (Protection of Human Subjects), and other federal, state and local regulations and guidance. NTI must receive the documentation that verifies IRB approval for this protocol, associated informed consent documents, and upon request, any recruitment material and handouts or surveys intended for the subjects, prior to the recruitment and enrollment of subjects.

Any amendments to the protocol or consent materials will be approved by the IRB before they are implemented. IRB review and approval will occur at least annually throughout the enrollment and follow-up of subjects and may cease if annual review is no longer required by applicable regulations. The site PI will notify the IRB of protocol deviations and reportable SAEs in accordance with IRB requirements.

